Not	e: Source verification critical settings made in InForm will over e: Collapsible settings are only available to users who have f	he rights to edit the item.	n Central Designer.		

Tria	athCone: Knee Society Score: Post-Op (POSTKS	S2011) [POSTKSS2011]
1. [*] ✔	Visit Date [Visit Date]	[KSSDOV] Req V / Req V / Req V (2015-2025)
2.* ✔	Height [Height]	[HT] xxxxx. Oinches [b] Ocentimeters
3.* ✔	Weight [Weight]	[WT] xxxxx. Olbs ^[b] kg
4.	BMI [read-only] [BMI]	[BMI] XXXXXXX.
5.* ✓	Charnley Functional Classification [Charnley Functional Classification]	[CHARNLY] A Unilateral Knee Arthritis B1 Unilateral TKA, opposite knee arthritic B2 Bilateral TKA C1 TKR, but remote arthritis affecting ambulation C2 TKR, but medical condition affecting ambulation C3 Unilateral or Bilateral TKA with Unilateral or Bilateral THR
Obje	ective Knee Indicators [POSTKSS_S2]	
6.* ✓	Alignment: measured on AP standing Xray (Anatomic Alignment) [Alignment]	[ALIGN] Neutral: 2-10 degrees valgus Varus: < 2 degrees valgus
7.* ✓	Medial / Lateral instability: measured in full extension [Medial / Lateral instability]	[INSTML] None Little or < 5 mm Moderate or 5 mm Severe or > 5 mm
8.* ✓	Anterior / Posterior Instability: measured at 90 degrees [Anterior / Posterior Instability]	[INSTAP] None Moderate < 5 mm Severe > 5 mm
9.* ✔	Range of motion [Range of motion]	[ROM] N3
10.* ✓	Flexion Contracture [Flexion Contracture]	[FLEXC] None 1-5 degrees 6-10 degrees 11-15 degrees > 15 degrees > 15 degrees
11.* ✓	Extensor Lag [Extensor Lag]	[EXTLAG] None <pre> </pre> <pre> <pre> <pre> <pre> <pre> <pre> <pre> <pre> <pre> <pre> <pre> <pre> <pre> <pre> <pre> <pre> <pre></pre></pre></pre></pre></pre></pre></pre></pre></pre></pre></pre></pre></pre></pre></pre></pre></pre>
Sym	ptoms [POSTKSS_S3]	-
12. [*] ✓	Pain with level walking [Pain with level walking]	[PNLVLWLK] 0 - None 1 2 3 4 5 6 7 8 9 10 - Severe
13.* ✓	Pain with stairs or inclines [Pain with stairs or inclines]	[PNSTAIR] 0 -
14. [*] ✓	Does this knee feel "Normal" to you? [Knee feels Normal]	[FEELNORM] Always Sometimes Never
Sub	ject Satisfaction [POSTKSS_S4]	Let #1
15. [*]	Currently, now satisfied are you with the pain level of your knee while sitting? [Satisfied with pain level of knee while sitting]	Very Satisfied Satisfied Neutral Dissatisfied Very Dissatisfied
16. [*] ✓	Currently, how satisfied are you with the pain level of your knee while lying in bed? [Satisfied with pain level of knee while lying in bed]	[INBED] Overy Satisfied OSatisfied ONeutral ODissatisfied Overy Dissatisfied
17. [*] ✔	Currently, how satisfied are you with your knee function while getting out of bed? [Satisfied with your knee function while getting out of bed]	[OUTBED] Very Satisfied Satisfied Neutral Dissatisfied Very Dissatisfied
18. [*] ✓	Currently, how satisfied are you with your knee function while performing light household duties? [Satisfied with your knee function while performing light household duties]	[HSEHLD] Very Satisfied Satisfied Neutral Dissatisfied Very Dissatisfied
19.* ✓	Currently, how satisfied are you with your knee function while performing leisure recreational activities? [Satisfied with your knee function while performing leisure recreational activities]	[RECACT] Very Satisfied Satisfied Neutral Dissatisfied Very Dissatisfied
Subj	ject Expectations [POSTKSS_S5]	
Com	pared to what you expected before your knee replacement:	
20.* ✓	My expectations for pain relief were [My expectations for pain relief were]	[EXPPR] Too High - "I'm a lot worse than I thought" Too High - "I'm somewhat worse than I thought"

[- lust Right - "My expectations were met"
		Too Low - "I'm somewhat better than I thought"
		Too Low - "I'm a lot better than I thought"
21.*	My expectations for being able to do my normal activities of daily	[EXPNORM]
~	[My expectations for being able to do my normal activities of daily	Too High - "I'm comewhat worse than I thought"
	living were]	
		Use Right - My expectations were met
		😳 Too Low - "I'm somewnat better than I thought"
		O Ioo Low - "I'm a lot better than I thought"
22.*	My expectations for being able to do my leisure, recreational or	[EXPLSRE]
~	sports activities were	Too High - "I'm a lot worse than I thought"
	[My expectations for being able to do my leisure, recreational or	Too High - "I'm somewhat worse than I thought"
		Just Right - "My expectations were met"
		Too Low - "I'm somewhat better than I thought"
		Too Low - "I'm a lot better than I thought"
Fund	tional Activities [POSTKSS_S6]	
23.*	Can you walk without any aids (such as a cane, crutches or wheelchair)?	
`	[Walk without any aids?]	
	ь. ,	
		[OTWLKAID]
		If no, which of the following aid(s) do you use?
		🖱 Wheelchair
		Walker
		Crutches
		Two canes
		One crutch
		One cane
		Knee sleeve / brace
		[KNFFATDS]
		Do you use these aid(s) because of your knees?
		O Yes
		ŇNO
. *	For how long one you should (with an without sid) hefore sitting due	
24.	For how long can you stand (with or without aid) before sitting due to knee discomfort?	[HLSTAND]
~	[How long stand before sitting?]	0-5 minutes
		6.15 minutes
		16 16 20 minutes
		10-30 minutes
		S1-60 minutes
		Omore than an hour
25.*	For how long can you walk (with or without aid) before stopping due	[HLWALK]
~	to knee discomfort?	O Cannot walk
		0-5 minutes
		O6-15 minutes
		16-30 minutes
		31-60 minutes
		OMore than an hour
How	much does your knee bother you during each of the following a	activities? [POSTKSS_S10]
26 *	Walking on an uneven surface	[UNEVEN]
✓.	[Walk on uneven surface]	No Slight Moderate Severe Very Cannot do (because I never do
		bother severe of knee) this
27.*	Turning or pivoting on your leg	[PIVOT]
~	[Iurn or pivot leg]	Slight Moderate Severe Very Cannot do (because I never do
28.*	Climbung up or down a flight of stairs	[UPDN]
~		bother severe of knee) this
*	Cathing up from a low south on a shair without arms	
29.	[Up from low couch or chair without arms]	ONo OSlight OModerate OSevere OVery OCannot do (because OI never do
•	is i d	bother severe of knee) this
30 *	Getting into or out of a car	[CARINOUT]
JU. ✔	[Get into or out of a car]	No Slight Moderate Severe Very Cannot do (because I never do
		bother severe of knee) this
31.*	Moving laterally (stepping to the side)	[MOVLAT]
~	[Move laterally]	ONO OSlight OModerate OSevere OVery OCannot do (because OI never do
		bother severe of knee) this
32.*	Climbing a ladder or step stool	[CLIMB]
~	[Climb ladder or step stool]	ONO OSlight OModerate OSevere OVery OCannot do (because OI never do
		DOTNER Severe of knee) this
33.*	Carrying a shopping bag for a block	[CARRY]
~	[Carry bag for a block]	ONO Slight Moderate Severe Very Cannot do (because I never do
		severe of knee) this
34.*	Squatting	[SQUAT]
~	[Squatting]	Slight Moderate Severe Very Cannot do (because I never do
35.*	Kneeling	[KNEELING]
~	[[bother of knee) this

36.* ✔	Running [Running]	[RUNNING] No Slight Moderate Severe Very severe Cannot do (because of knee) I never do this
Disc	etionary Knee Activities [POSTKSS_S9]	
37.* ✓	Discretionary Knee Activity 1 [Discretionary Knee Activity 1]	[cmpDISCACT1] [DISCACT1] Discretionary Knee Activities [cl_DISCACT] ▼ [BOTHER1] How much does your knee bother you during this activity? No bother Slight Moderate Severe Very severe Cannot do (because of knee)
38.* ✓	Discretionary Knee Activity 2 [Discretionary Knee Activity 2]	[cmpDISCACT2] [DISCACT2] Discretionary Knee Activities [cl_DISCACT] ♥ [BOTHER2] How much does your knee bother you during this activity? No bother Slight Moderate Severe Very severe Cannot do (because of knee)
39.* ✓	Discretionary Knee Activity 3 [Discretionary Knee Activity 3]	[cmpDISCACT3] [DISCACT3] Discretionary Knee Activities [cl_DISCACT] ♥ [BOTHER3] How much does your knee bother you during this activity? No bother Slight Moderate Severe Very severe Cannot do (because of knee)
40. ✔	Comments [Comments]	[KSSCOM] A200
41.	Alignment [read-only] [Alignment]	[ALIGNSC] XXXXXXX.
42.	Instability [read-only] [Instability]	[INSTSC] xxxxxxx.
43.	Joint Motion [read-only] [Joint Motion]	[JOINTSC] xxxxxxx.
44.	Symptoms [read-only] [Symptoms]	[SYMPSC] xxxxxxx.
45.	Subject Satisfaction Score [read-only] [Subject Satisfaction Score]	[SATSC] xxxxxxx.
46.	Subject Expectations [read-only] [Subject Expectations]	[EXPSC] xxxxxxx.
47.	Walking and Standing [read-only] [Walking and Standing]	[WLKSTSC] xxxxxxx.
48.	Standard Activities [read-only] [Standard Activities]	[STDACTSC] xxxxxxx.
49.	Advanced Activities [read-only] [Advanced Activities]	
50.	Discretionary Knee Activities [read-only] [Discretionary Knee Activities]	
51.	Ubjective Knee Score [read-only] [Objective Knee Score]	
52.	Functional Knee Score [read-only] [Functional Knee Score]	
Key	$[\lor] =$ Source verification required [b] = Base Unit [] Item is collapsi	ble

Note: Source verification critical settings made in InForm will override any settings made i Note: Collapsible settings are only available to users who have the rights to edit the item. Central Designer.

Т	TriathCone: Post-Op Events (POEVENT) [POEVENT]			
1. •	Visit Date [Visit Date]	[VSDT] Req V / Req V (2015-2025)		
2. •	Have there been any protocol defined Adverse Events since the last visit?	[PROTAE] Ves		
	*If Yes, complete an AE form for each event. [Protocol defined Adverse Events]	© No		
3.*	Has the subject seen a doctor for any medical event since the last visit? [Seen doctor for medical event since last visit]	[SEEDOC] Yes [SEEDOCY] If Yes, specify A1000		
4.**	Has the subject been hospitalized for any elective surgery since the last visit? [Subject hospitalized for elective surgery since last visit]	[HOSP] [Contralateral knee Contralateral hip [Dislateral hip [Contralateral shoulder [Insilateral shoulder [Contralateral shoulder [Details] Provide [Contralateral shoulder [Contralateral shoulder [Contralateral shoulder		
5.	Is anything currently affecting the subject's function? [Is anything currently affecting the subjects function]	No [AFFUNC] [CmpAFFUNC] □ Yes [AFUNCY] Specify A1000		

		© No	
6.	Comments		
	[comments]	A200	
K	ey: [] = Source verification required [] = Item is collapsible ote: Source verification critical settings made in InForm will override a ote: Collapsible settings are only available to users who have the right	, any settings made in Central Designer. Is to edit the item.	

Tria	athCone:	Adverse E	vent Tria	thCone (AE) - Repe	ating Form [A	E]				
# S	eq Onset	When did	Adverse	System	Descril	be Device	- Meet protocol definition	Treatment	Resolution of	Comments	Other
r	lo Date	event occur?	Event	Organ Class	circumsta	nces Related	of seriousness		event		Treatments
1											
Adv	erse Event T	riathCone [AE]								
1.	Seq No. [rea	ad-only]			[AESEC	2NO]					
62	[Seq No]				N2						
2 *	Onset Date				[AESTE	DAT]					
✓	[Onset Date]			Req 🗸	/ Req 🗸 / Req 🗸	(2015-2025)					
\$											
3.*	When did ev	ent occur?			[AEWH	IEN]					
~	[When did e	vent occur?]			OPred	operative					
					OPeri	toporativo	rative to nospital discharge)				
					UFUS						
4.*	Adverse Eve	ent] profibrocic					
`		enej				n loint Infection					
					-Exc	essive Knee Pain					
						noral Fracture					
					_[cm	pLOOSFC] 🖃					
					Loo	sening Femoral Com	ponent				
						Septic					
					ŏ	Aseptic					
					() [cm	pLOOSPC] 🖃					
					Loo	sening Patellar Comp OSPC1	oonent				
						Septic					
					ŏ,	Aseptic					
					()[cm	pLOOSTB] 📃					
					Loo	sening Tibial Compoi	nent				
					09	Septic					
					0/	Aseptic					
					OMyc	ositis Ossificans					
					O Pate	ellar Component Disi ellar Fracture	ocation				
					OPate	ellar Subluxation					
					ÖPate	ellar Tendon Rupture	1				
					Pero	oneal Nerve Palsy					
					OPros	sthesis Fracture / Fe	moral Component				
					Pros	sthesis Fracture / Pa	tellar Component				
					O Pros	sthesis Fracture / Tib	vial Component				
					O Refl	lex Sympathetic Dys	tronhy (RSD)				
					Soft	t Tissue Trauma					
					Sup	erficial Wound Infect	tion				
					ŌSup	racondylar Fracture					
					Tibi	al Component Subsid	dence				
					OTibi	al Fracture					
					Woi	und Related					
					[AE (Sp	WOUND] ecify)					
					A20	00					
					[cm	pOPSITEOT] 📃					
					Ope	erative Site Other					
					[OP	SITEOT]					
					A20	00					
					[cm	pAERESP] 🖃					
					Bro	nchopulmonary					
					[AE	RESP] ecify)					
					A20	00					
					() [cm	pAECA] 📃					
					Can	cinoma					
					[AE (Sp)	CA] ecify)					
					A20	00					
	-										

		Cardiovascular [AECARD] (Specify) A200 DVT [cmpAEDERM] □ Dermatological [AEDERM] (Specify) A200 [cmpAEGASTRO] □ Gastrointestinal [AEGASTRO] (Specify) A200 [cmpAEGASTRO] □ Gastrointestinal [AEGASTRO] (Specify) A200	
		Genicourinary [AEURO] (Specify) A200 [cmpAENEURO] □ Neurosensory [AENEURO] (Specify) A200	
		Pulmonary Embolism ○ Thrombophlebitis ○ [cmpAETRAUMA] □ Trauma [AETRAUMA] (Specify) A200 ○ [cmpOTSYS] □ Systemic Other	
5.* •	System Organ Class [System Organ Class]	[OTSYS] (Specify) A200 [soc] [clSoC] v	
6.* *	Describe circumstances, including history or causative event, specify signs, symptoms and diseases [Describe circumstances]	[AECIRCUM] A1000	
7.* ✓	Device Related? [Device Related]	[DVREL] ©[cmpDEVY]	

		Yes DEVRELY] If Yes or Uncertain, specify below, contact Stryker within 24 hours and send de-identified source documentation. No CompDEVU] Uncertain DevReLU] If Yes or Uncertain, specify below, contact Stryker within 24 hours and send de-identified source documentation. A1000	
8.* ✓	Seriousness - Does this event meet the protocol definition of seriousness? [Meet protocol definition of seriousness]	[AESER] [ImpAESER] □ Yes [AESERY] If Yes, check all that apply Resulted in inpatient hospitalization Resulted in persistent or significant disability/incapacity Resulted in permanent impairment of a body function or permanent damage to a body structure Necessitated medical or surgical intervention to preclude permanent impairment of a body function or permanent damage to a body structure Was a life threatening situation Resulted in subject death [AESERDT] Specify when Adverse Event became Serious. If Serious date is the same as Onset Date, enter Onset Date No	
9.* ✓	Treatment Contact Stryker within 24 hours if the treatment is Revision/Removal or Re-Operation For Stryker Implants, submit PER form and implant(s) to Stryker. Reoperations are for study knee only and include open manipulation/reduction. Do not include revision/removals or operations unrelated to the study knee. Other Treatments: Diagnostic tests are not considered Treatments (i.e. X-rays and MRIs should NOT be included) [Treatment]	[AETX] [TXTYPE] □ Yes [ReVisions/Removals [FEMDT] Femoral Component Date Req ♥ / Req ♥ / Req ♥ (2015-2025) [FCAUGDT] Femoral Cone Augment Date Req ♥ / Req ♥ / Req ♥ (2015-2025) [Tibal Baseplate Date Req ♥ / Req ♥ / Req ♥ (2015-2025) [TCAUGDT] Tibial Cone Augment Date Req ♥ / Req ♥ / Req ♥ (2015-2025) [TCAUGDT] Tibial Cone Augment Date Req ♥ / Req ♥ / Req ♥ (2015-2025) [INSRTDT] Tibial Insert Date Req ♥ / Req ♥ / Req ♥ (2015-2025) [INSRTDT] Tibial Insert Date Req ♥ / Req ♥ / Req ♥ (2015-2025)	

		Contraction of the second seco	Patellar Component Date Req V / Req V / Req V (2015-2025) Soperations [cmpREOP1] = Reoperation 1 [REOP1DT] Date Req V / Req V / Req V (2015-2025) [REOP1SP] Specify A200 [mpREOP2] = Reoperation 2 [REOP2DT] Date Req V / Req V (2015-2025) [REOP2SP] Specify A200 [mpREOP3] = Reoperation 3 [REOP3DT]
			Date Req V / Req V / Req V (2015-2025)
			Specify A200
		Oth ONo	er Treatments
10.* ✓	Resolution of event [Resolution of event]	[RESOL] [cmpU Unreso [UNRE Unreso Req [cmpR Resolv [RESD Resolu Req V	NRESDT] blved sDT] blved Status Date (Update the resolution if the Event has been resolved) / Req / Req (2015-2025) ESDT] ed tion status date / Req (2015-2025)
11. ✓	Comments [Comments]	[AECOMM	NT]
		1200	
	Other Treatments		Other Treatment Date
12. ✓			
Othe	r Treatments Entry [AE_S5]	1	
12.1* ✓	[Other Treatments]		אדזכ 200
12.2* ✓	Date [Other Treatment Date]	E F	DTXDT] Leq V / Req V (2015-2025)
Key: Note Note	: [*] = Item is required [] = Source verification required [] = : Source verification critical settings made in InForm will override any : Collapsible settings are only available to users who have the rights	Item is coll settings m to edit the i	apsible [%] = Key item ade in Central Designer. tem.

Tr	TriathCone: Study Termination (TERM) [TERM]			
GE	NERAL INFORMATION [TERM_S1]			
1. [*] ✔	TERMINATION DATE [TERMINATION DATE]	[TERMDT] Req V / Req V (2015-2025)		
ST	UDY TERMINATION [TERM_S2]	-		
2.* ✔	DID SUBJECT COMPLETE STUDY ACCORDING TO PROTOCOL?	COMPLET] Yes No		
	[Subject complete study]			
3.	PROTOCOL? Click for eHelp [Subject complete study] CHECK ONE PRIMARY REASON Click for eHelp [Reason subject did not complete study]	00 [RI 0000	Yes No ASON] Screen Failure Death Investigative site terminated [monLOSTEVP] Lost to follow-up [STLE] List efforts to contact subject: [STD1] List efforts contact subject: [STD2] List efforts con	
		00	Subject Withdrawal [cmpSURGNOT] Surgery Not Performed [Specify) A1000	

4.* ✓	WAS STUDY DEVICE IN PLACE AT DATE OF LAST CONTACT? [WAS STUDY DEVICE IN PLACE AT DATE OF LAST CONTACT]	[DEVICE] O Yes O No
со	MMENTS [TERM_S3]	
5. ✔	Comments [Comments]	[TERMCOM] A200

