	System with at least one Triathlon Tritanium Cone Augment. The	
	clinical outcomes of Triathlon Tritanium Cone Augments will be	
	compared to published literature and data collected in the Triathlon TS	
	Outcomes Study.	
	1. Follow-up of each revision TKA case to 5 years	
Study Duration	2. Enrollment period of 48 months	
	3. Approximate 10-year total duration	
Number of Centers	8 to 12 investigational centers	
	The revision rate of the Triathlon Tritanium Cone Augments is expected	
Hypothesis	to be less than 2.8% for a septic loosening ^{$1,2$} of either the Femoral or the	
	Tibial Cone Augments at 2 years postoperative.	

	Primary:
	To evaluate the success rate of the Triathlon Tritanium Cone Augment
	with the Triathlon TS Total Knee System at 2 years postoperative,
	defined as absence of revision of the Femoral Cone Augment or Tibial
	Cone Augment for aseptic loosening.
	Secondary:
	To evaluate unexpected end-of-stem pain with regards to the
	Triathlon Tritanium Cone Augments location and severity and
Objectives	compare to published literature ³ at 2 years postoperative.
	To evaluate intraoperative bone defects using the Anderson
	Orthopaedic Research Institute (AORI) classification and correlate
	with the size and shape of cone implanted ^{6,7} .
	Exploratory:
	To evaluate the mean KSS objective knee scores at 2 years
	postoperative for cases which received the Triathlon TS Total Knee
	System with a Triathlon Tritanium Central Femoral Cone Augment.

	Function and health related quality of life (QOL) will be compared
	between the Triathlon TS with Triathlon Tritanium Cone Augments
	and published results for other revision knee systems with
	metaphyseal augments, as well as the Triathlon TS Outcomes
	Study using the following outcomes measures:
	 2011 Knee Society Score (KSS)⁹
	 Short Form-12 (SF-12)
	 Lower Extremity Activity Scale (LEAS)
	 Hospital for Special Surgery (HSS) Patella Score
Additional Data	 ○ EuroQuol 5D (EQ-5D)
Collection	 Follow-Up Questionnaire
	• Data collected at 6-week, 6-month, 1-year, 2-year, and 5-year
	visits will be compared to above mentioned controls with respect to
	improvement from preoperative scores.
	Radiographic stability, preoperative AORI classification and
	complications will be compared between those implanted with the
	Triathlon TS with Triathlon Tritanium Cone Augments and
	published results for other revision knee systems.
	Surgical details will be compared to data collected as part of the

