8.4 Statistical Methodology

8.4.1 Data Summary

Descriptive statistics will be computed for all baseline conditions and demographic parameters. That is, for continuous data, the N, mean, median, standard deviation, minimum and maximum will be computed. For categorical data, the frequency will be computed. The data will be presented by appropriate subgroups (e.g., center).

For all additional data collected that are not required for direct support of a study objective, data will be summarized according to visit. For parameters represented by continuous variables (e.g., ROM), the summaries will consist of the N, mean, median, standard deviation, minimum, and maximum values. For categorical variables (e.g.,gender), the frequency and percentage in each category will be presented.

A two way table of preoperative AORI classification by femoral or tibial cone augment size will be presented.

A table of shin pain by thigh pain will be created separately for cases with femoral cone augment implanted only, tibial cone augment implanted only, and both femoral cone augment and tibial cone augment implanted at preoperative, 6 weeks, 2 years, and 5 years.

LEAS at 2 years will be compared to the Triathlon TS Outcomes Study as reported at 2 years postoperative, adjusted by preoperative LEAS, age, gender, and BMI, if applicable. The improvement from preoperative visit to postoperative visits will be compared with the Triathlon TS Outcomes Study, if applicable.

The HSS Patella Score at 2 years postoperative will be compared to the Triathlon TS Outcomes Study as reported at 2 years postoperative, adjusted by preoperative HSS Patella Score, age, gender, and BMI, if applicable. The improvement from preoperative visit to postoperative visits will be compared with the Triathlon TS Outcomes Study if applicable.

Statistical analyses including T-test, Wilcoxon test or Chi-square tests will be utilized for comparing the applicable surgical data collected from Triathlon TS Outcomes Study.

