Appendix G

Draft Specifications for Electronic Case Report Forms

Annotated Study Book for Study Design: TriathCone

Study Design Version: 1.4

Sponsor: Stryker

Protocol: TriathCone

A prospective, post-market, multi-center evaluation of the clinical outcomes of the Triathlon TS Total Knee System with Triathlon Tritanium Cone Augments

Generated by Central Designer TM

May 8, 2015 5:20PM

	Element		Sys	tem									
	Assessment	CRF	System Screening (SCR) [S]	System Enrollment (ENR) [S]	Baseline / Pre- Op (BASE/PREOP) [S]	Surgical Details (INTRAOP) [S]	6WK (6WK) [S/D]	6MO (6MO) [S/D]	1YR (1YR) [S/D]	2YR (2YR) [S/D]	5YR (5YR) [S/D]	Adverse Event (AE) [S]	Study Completion (STUDYCOMP) [S]
	Visit Start Hours		0	0	0	1	1009	5041	9409	18169	18170	18171	18172
1	System Screening	SCR	1										
2	System Enrollment	ENR		1									
3	Date of Visit	DOV			1	1	1	1	1	1	1		
4	Inclusion / Exclusion	IE			2								
5	Demographics	DM			3								
6	CENSOR	CENSOR			4								
7	Knee Society Score: Pre-Op	PREKSS2011			5								
8	SF-12v2 Health Survey	SF12			6		4	4	4	4	4		
9	Lower Extremity Activity Scale	LEAS			7		5	5	5	5	5		
10	HSS Patella Score	HSSPAT			8		6	6	6	6	6		
11	EQ-5D Health Questionnaire	EQ5D			9		7	7	7	7	7		
12	End of Stem Pain	ESP			10		8			8	8		
13	Previous Implant Information	PIF				2							
14	Surgical Details	SURG				3							
15	Surgical Prostheses	SP				4							
16	Knee Society Score: Post-Op	POSTKSS2011					2	2	2	2	2		
17	Post-Op Events	POEVENT					3-DF	3-DF	3-DF	3-DF	3-DF		
18	Adverse Event TriathCone	AE										1-RF	
19	Study Termination	TERM											1

Tr	FriathCone: System Screening (SCR) [SCR]				
1. [*] ✓	Subject Initials [Subj Initials]	[SCRIN] Enter "- A3	T] ", if subject does not have a middle initial.		
ĸ	ey: $[*] =$ Item is required $[\checkmark] =$ Source verification required				

Note: Source verification critical settings made in InForm will override any settings made in Central Designer.

Т	TriathCone: System Enrollment (ENR) [ENR]				
1.	Subject Number [read-only] [Subj Number]	[SUBID] A10			
2. ✓	* Scheduled Surgery Date [Scheduled Surgery Date]	[SCHDSURG] Req v / Req v (2015-2025)			
	Key: [*] = Item is required [✓] = Source verification required Note: Source verification critical settings made in InForm will override any settings made in Central Designer.				

TriathCone: DOV (DOV) [DOV]			
1.*	Date of Visit [Date of Visit]	[DOVDT] Req V / Req V / Req (2015-2025)	
Kev: [*] = Item is required			

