4. [*] ✔	Joint Line Position Prior to Implant Removal: Full Extension [Joint Line Position Prior to Implant Removal: Full Extension]	[PRIORFULL] N4 mm ^[b]		
5. [*] ✔	Joint Line Position Prior to Implant Removal: 90 degree Flexion [Joint Line Position Prior to Implant Removal: 90 degree Flexion]	[PRIOR90] N4 mm ^[b]		
6.* ✔	Joint Line Position Final Triathlon Cone implanted: Full Extension [Joint Line Position Final Triathlon Cone implanted: Full Extension]	[FINALFULL] N4 mm ^[b]		
7.* ✓	Joint Line Position Final Triathlon Cone implanted: 90 degree Flexion [Joint Line Position Final Triathlon Cone implanted: 90 degree Flexion]	[FINAL90] N4 mm ^[b]		
8.* ✓	Tibial AORI Classification [Tibial AORI]	[TAORI] Type I Type IIa Type IIb Type III		
9.* ✓	Femoral AORI Classification [Femoral AORI]	[FAORI] Type I Type IIa Type IIb Type III		
10.* ✔	Navigation Used [Navigation Used]	[NAVIGATION] Yes No		
11. [*] ✓	Estimated blood loss [Estimated blood loss]	[BLOSS] N4 cc's		
12. [*] ✔	Units of blood transfused [Units of blood transfused]	[UNITRANS] N4 cc's		
13. [*] ✔	Skin to skin time [Skin to skin time]	[SKTOSK] N3 minutes		
14. [*] ✓	Tourniquet time [Tourniquet time]	TOURN Minutes		
15.* ✔	Tibio-Femoral Gap, Full Extension: Medial [Tibio-Femoral Gap, Full Extension: Medial]	[GAPFLMED] N2 mm ^[b]		
16. [*] ✔	Tibio-Femoral Gap, Full Extension: Lateral [Tibio-Femoral Gap, Full Extension: Lateral]	[GAPFLLAT] N2 mm ^[b]		
17. [*] ✔	Tibio-Femoral Gap, 90 degree Flexion: Medial [Tibio-Femoral Gap, 90 degree Flexion: Medial]	[GAP90MED] N2 mm ^[b]		
18.* ✓	Tibio-Femoral Gap, 90 degree Flexion: Lateral [Tibio-Femoral Gap, 90 degree Flexion: Lateral]	[GAP90LAT] N2 mm ^[b]		
19.** •	Tibial Bone Loss?]	[BLOSSTIB]		

20.*	Femoral Bone Loss? [Femoral Bone Loss?]	[BLOSSFEM] © [cmpFEMLOC] □ Yes [FEMLOC] □ [cmpAF] □ Anterior Femur [AFCONTAIN] Anterior femur defect contained? Yes No □ [cmpCC] □ Central [CCONTAIN] Central defect contained? Yes No □ [cmpMD] □ Medial Distal Femur [MDCONTAIN] Medial Distal Femur defect contained? Yes No □ [cmpLD] □ Lateral Distal Femur
*	Race Demound: Dictal Formur	Lateral Distal Femur defect contained? Yes No [cmpLP]
21. ✓	[Bone Removed: Distal Femur]	N3 mm ^[b]
22.* ✓	Bone Removed: Proximal Femur [Bone Removed: Proximal Femur]	[REMOVDF] N3 mm ^[b]
23.* ✓	Distal Femoral Coverage [Distal Femoral Coverage]	[DISTFMR] Complete [mmpUNS2] □ Undersized [UNDERS2] N2 mm ^[b] Overhang [OVHANG] N2 mm ^[b]

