24.* ✓	Posterior Condyles: Overhanging bone removed prior to final implant? [Posterior Condyles: Overhang bone removed prior to final implant]	[PCONDYL] Yes No
25.* ✓	Proximal Tibia: AP Coverage Complete? [Proximal Tibia: AP Coverage Complete?]	[APCOMP] Yes [UNOVAP] No [cmpANTPOS1] = Undersized [ANT1] Anterior N2 mm ^[b] [POS1] Posterior N2 mm ^[b] [cmpANTPOS2] = Overhang [ANT2] Anterior N2 mm ^[b] [cmpANTPOS2] = Overhang [ANT2] Anterior N2 mm ^[b] [POS2] [POS2] Posterior N2 mm ^[b] [POS2] Posterior N2 mm ^[b] [POS2] Posterior N2 mm ^[b]
∠6.* ✓	[Proximal Tibia: ML Coverage Complete?]	Yes [UmpWEDLAT1] Undersized [MEDLAT1] [MED1] Medial N2 mm[b] [CmpMEDLAT2] Overhang [MED2] Medial N2 mm[b] [LAT2] Medial N2 mm[b] Lateral N2 mm[b]

27.* •	How satisfied are you with the fit? [How satisfied with fit]	[SATFIT] © Extremely © Quite a bit © Moderately © A little bit © Not at all		
28.* ✓	Intraoperative complication? (If yes, complete AE form.) [Intraoperative complication]	[COMPL] ①Yes ②No		
29. [*] ✔	Post-op plan [Post-op plan]	[POSTPLAN] Tull weight bearing Partial weight bearing		
30.* ✓	Discharge to [Discharge to]	[DISCHRG] Skilled Nursing Facility Chronic Care Center Rehabilitation Unit Home [mpOTDIS] □ Other [OTDIS] Specify A100		
31. [*] ✔	Discharge Date [Discharge Date]	[SDDISDT] Req 💟 / Req 💟 / Req 💟 (2015-2025)		
32.	Length of Hospital Stay [read-only] [Length of Hospital Stay]	[STAY] N3 Days ^[b]		
33. ✓	Comments [Surgery Comments] :: [♥] = Source verification required [b] = Base Unit []] = Item is collap :: Source verification estical attings mode in InSerm will superification estical	[SURGCOM] A200 sible or mode in Control Decisions		
Not	Note: Collapsible settings are only available to users who have the rights to edit the item.			

Tria	athCone: Surgical Prostheses (SP) [SP]			
СОМ	PONENT LISTING [SP_S1]				
1.* ✓	Femoral Component [Femoral Component]	[cmpFC] Femoral Component Reference # [clFREF] [clFREF]			
		Femoral Component Lot	A50		
2. ✓	Femoral Cone Augment	[cmpFCA]		[FCONEREF]	
		Femoral Cone Au [FCONELOT]	ugment Refere	ence # [ciFCREF]	
		Augment Lot #	A50		
3.* ✓	Tibial Component/Metal Tray [Tibial Component/Metal Tray]	[cmpTC] Tibial Componen	it/Metal Tray F	Reference # [clTIBIREF]	
		[TIBLOT] Tibial Component/Meta Tray Lot #	al A50		
4. ✓	Tibial Cone Augment [Tibial Cone Augment]	[cmpTCA] Tibial Cone Augr	nent Referenc	[TCONEREF] e # [clTCREF]	
		[TCONELOT] Tibial Cone Augment Lot #	A50		

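### Two required Surgical Details items in the Appendix G eCRF specification are mislabelled or ambiguous: the scale for transfused blood (item 12) and the anatomical site of bone removed (item 22)

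*Combined protocol and SAP*

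**What the plan says.** **Item 12** of Surgical Details (Appendix G) is labelled "Units of blood transfused [Units of blood transfused". Its field is printed as "UNITRANS] N4 cc's": a four-digit number with a volume unit, the same format as item 11, estimated blood loss.

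**Items 21 and 22** ask for the amount of bone removed. Item 21 is "Bone Removed: Distal Femur". Item 22 is "Bone Removed: Proximal Femur [Bone Removed: Proximal Femur", a three-digit number in mm, with the variable name REMOVDF printed beside it.

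Both 12 and 22 carry an asterisk and the source-verification tick. The keys on other forms in the same appendix, such as System Screening, define the asterisk: "Key: [*] = Item is required". Section 7.4 adds that all requested data must be documented and any gap explained.

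On use, the Study Synopsis (Additional Data Collection) says: "Surgical details will be compared to data collected as part of the" Triathlon TS Outcomes Study. Section 8.4.1 says that t-tests, Wilcoxon tests or chi-square tests "will be utilized for comparing the applicable surgical data collected from Triathlon TS Outcomes Study". The same section summarises additional data that do not directly support an objective, using N, mean, median, standard deviation, minimum and maximum for continuous variables.

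**The concern.** In item 12 the label asks for a count and the field asks for a volume. Nothing legible on the form says which governs, so one centre may enter a number of bags and another a number of cc's.

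In item 22 the proximal femur is the hip end of the bone. A measurement of bone removed there has no evident meaning in a revision knee procedure. A centre must nevertheless enter a value or explain a blank, and whatever it enters cannot be attributed to a known anatomical site.

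At stake are two descriptive surgical variables and any between-study comparison that uses them. Section 10 allows surgical information to be published before the 2-year time point, so these variables could be reported early.

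**Working it through.** The plan gives no figure to reproduce, and no sample size, power or margin depends on these items. The check sets the form entries side by side, with one short calculation for item 12.

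**Item 12: size of the ambiguity.** The documents give no volume per unit, so I assume c = 300 to 500 cc.

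- A transfusion of 2 units can be entered as 2 (a count), or as 2 × 300 = 600 to 2 × 500 = 1,000 (a volume). A four-digit field accepts all of these.
- Suppose a share f of transfused cases is entered as counts, unrelated to the amount given. The recorded mean is then the true mean volume × [1 − f(1 − 1/c)].
- With c = 300, 1 − 1/300 = 0.997. With c = 500, 1 − 1/500 = 0.998. The mean therefore falls by almost exactly the fraction f, and the assumed volume per unit hardly matters.
- Cases with no transfusion are unaffected, because zero is the same on both scales.

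**Item 22: what site could be meant?**

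| Evidence on the form | Points towards |
|---|---|
| Item 21 already covers the distal femur | a different site for item 22 |
| The other proximal site named is the proximal tibia (items 25 and 26, coverage only) | proximal tibia |
| No legible item records an amount of tibial bone removed | proximal tibia |
| Items 20, 21, 23 and 24 are all femoral; item 24 is "Posterior Condyles: Overhanging bone removed prior to final implant" | another femoral site |
| The variable name REMOVDF reads like distal femur | a femoral site, or a name belonging to item 21 |

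Two cautions apply. The page is poorly legible here: item 21's variable name cannot be read, so REMOVDF may have shifted from its own line, and the response block under item 19 (tibial bone loss) is not visible. The label also fails under every row of the table: whether a tibial or another femoral site was meant, the printed words are wrong.

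**Where the values go.** The primary endpoint is revision or removal of a cone for aseptic loosening (8.1.1). The secondary parameters are end-of-stem pain, and AORI class with cone size and shape (8.1.2); AORI class comes from items 8 and 9. The exploratory parameter is the KSS objective knee score (8.1.3). None uses item 12 or 22. Both fall under the descriptive summaries of 8.4.1 and may fall under its comparison of surgical data.

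**The case against.** **Cc entries are usable and mixed entries can mostly be told apart.** This stands. The unit is printed next to the field, and a count of 2 does not overlap with 600 to 1,000. A reader might infer that item 12 cannot give usable data, or that the two scales could never be separated afterwards; neither follows. Source verification (7.3, 9.1) and queries (7.5) could catch many errors. However, the plan has no rule for doing so, and monitors checking against an ambiguous label may accept either entry.

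**The tibia is a guess.** This also stands. A reader might conclude that item 22 is simply a misprint for the proximal tibia. The documents never state the intended site, and the neighbouring items and printed variable name are femoral. Only a request to clarify the site is supported.

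**The form is an old draft.** Appendix G is titled as draft specifications and was generated in May 2015. It excludes BMI above 40 where the Synopsis says above 45, so it has not been kept in step with the protocol. The live eCRF cannot be seen, and it may already be correct. Yet the current protocol, which cites an August 2019 device clearance (3.1), still carries this form as its specification, and 8.4.2 refers to existing data from this study. Checking the live form is therefore warranted.

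**No effect on the comparison is shown.** Section 8.4.1 limits the tests to applicable surgical data and names no variables. The earlier study's form is not in the documents, and Table 1 mentions neither transfusion nor amount of bone removed. It would go too far to say that the between-study comparison is compromised. The descriptive summaries in 8.4.1 do not depend on that restriction.

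**Conclusion.** The point holds as a minor data-collection defect. Item 12's label and unit conflict, and item 22 names an anatomical site that does not fit the operation. If the live eCRF matches Appendix G:

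- the mean transfusion volume falls by about the share of transfused cases entered as counts (assuming 300 to 500 cc per unit, with the coding unrelated to the amount given);
- item 22 is uninterpretable for every case entered under that label, in a study of at least 145 cases, until the site is clarified.

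A reader might infer that the study's account of metaphyseal bone loss is damaged. The documents do not support that. Bone loss is recorded by AORI class (items 8 and 9) and by the bone-loss items (19 and 20), and no primary, secondary or exploratory endpoint is affected. The consequence is limited to the descriptive summaries of these two variables and to any comparison with the earlier study that chooses to use them.

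**What to change.** 1. **Item 12:** use one scale in both label and unit: either *Volume of blood transfused, cc*, or a count of units with the cc's removed. Match it to the earlier study's form.
2. **Item 22:** have the sponsor confirm the intended anatomical site. Then correct the label, and the variable name if it proves to be wrong. Do not relabel it to the tibia without that confirmation.
3. **Live eCRF:** check both items. If the live labels are already correct, only the appendix needs updating. If they match Appendix G, query existing entries before they are summarised or compared.

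The cost is two form edits and, if needed, one round of queries. Sample size, endpoints and analysis methods do not change.
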